7.2 Statistical Methods

Primary endpoint (adherence). We will compute the proportion of patients who are adherent to the diet restriction (as defined in section 3.2), along with a 95% exact confidence interval. We will also use an exact binomial test (with a one-sided alpha of 0.05) to test whether adherence is greater than 60%.

Aim 1b. We will compute the proportion of patients with toxicity, along with a 95% exact confidence interval. Our institution's historical toxicity rate among similar patients is about 80% and we aim to prove that the dietary intervention is non-inferior with an absolute margin of 10%, using an exact binomial test. With a total sample size of 90 and assuming that true toxicity will be 80% or lower, we have 82% power (with one-sided alpha of 0.05).

Secondary endpoints. The change in body fat measurement between baseline and the end of the study will be analyzed via a paired t-test. Weight changes over time will be assessed by modeling BMI as a function of time (baseline, diet weeks 1, 3, 5, 7, and 10) via mixed-effects regression. The patterns of change over time in vital signs, insulin and other clinical labs, serum markers, and psycho-social outcomes (FACT-B) will also be analyzed similarly. If some of these measures are skewed, we will transform them (e.g., log) before the analyses. Finally, local recurrence, distant metastases, progression free survival, and overall survival will be analyzed via survival methods, specifically the Kaplan-Meier method and the logrank test. If sufficient events occur, we may assess the impact of various patient and clinical/treatment variables on these outcomes via Cox proportional hazards regression.

Local recurrence, progression free survival, distant metastases and overall survival will be assessed and compared with historic controls using the Kaplan Meier method. Local recurrence, progression free survival, distant metastases and overall survival will be measured from the date of study enrollment to time of event.

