-------------------	---

Number of Subjects	90
Diagnosis and Main Inclusion Criteria	Patients with DCIS or invasive breast cancer who will receive radiation and are appropriate candidates for breast conservation to be treated to the whole breast
Study Therapy, Dose, Route, Regimen	Radiation and Caloric Restriction: a 25% reduction in total caloric intake
Duration of administration and follow-up	Caloric Restriction for 10weeks (2weeks minimum prior to radiation, during 6-6.5 weeks of radiation and 2 weeks minimum after for a total of at least 10weeks) with a follow up visit 4 weeks after treatment completion.
Reference therapy	Patients acute toxicity on this trial will be compared with historic controls of other patients who received 6-6.5 weeks of radiation at Bodine Cancer Center
Statistical Methodology	The study will enroll a total of 90 patients. Phase 1: With a sample size of 40, the study has 83% power to establish that adherence is higher than 60%, assuming that true adherence will be 80% or greater (one-sided exact binomial test with alpha 0.05). Phase 2: We will compute the proportion of patients with toxicity, along with a 95% exact confidence interval. Our institution's historical toxicity rate among similar patients is about 80% and we aim to prove that the dietary intervention is non-inferior with an absolute margin of 10%, using an exact binomial test. With a total sample size of 90 and assuming that true toxicity will be 80% or lower, we have 82% power (with one-sided alpha of 0.05).

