7 STATISTICAL PLAN

7.1 Sample Size Determination

The study will enroll a total of 90 patients. For Phase 1, with a sample size of 40, the study has 83% power to establish that adherence is higher than 60%, assuming that true adherence will be 80% or greater (one-sided exact binomial test with alpha 0.05).

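### Does a 95% exact interval beside a one-sided 5% exact test leave the two primary conclusions in doubt?

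*Combined protocol and SAP*

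**What the plan says.** Section 7.2 (Statistical Methods) gives each primary endpoint an estimate and a test.

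- **Adherence, estimate:** the sentence that plans the interval reads, up to its last word, "We will compute the proportion of patients who are adherent to the diet restriction (as defined in section 3.2), along with a 95% exact confidence".
- **Adherence, test:** the plan then turns to the hypothesis: "We will also use an exact binomial test (with a one-sided alpha of 0.05) to test whether adherence is greater than 60" per cent. Section 7.1 ties the power to that test: "with a sample size of 40, the study has 83% power to establish that adherence is higher than 60" per cent. The condition attached to this figure is "assuming that true adherence will be 80% or greater (one-sided exact binomial test with alpha 0.05".
- **Toxicity (Aim 1b), estimate:** "We will compute the proportion of patients with toxicity, along with a 95% exact confidence interval".
- **Toxicity, test:** the reference rate is given as "Our institution's historical toxicity rate among similar patients is about 80" per cent. The claim to be made is "we aim to prove that the dietary intervention is non-inferior with an absolute margin of 10%, using an exact binomial test". The stated power is 82% with 90 patients, a true rate of 80% or lower and one-sided alpha 0.05.

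The Study Summary repeats both tests (for adherence, "one-sided exact binomial test with alpha 0.05") and the toxicity interval. It mentions no interval for adherence. Nowhere does the document say whether the intervals are one- or two-sided, or what happens if interval and test point in different directions.

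**The concern.** Read in the usual way, a 95% exact interval is two-sided, with 2.5% in each tail. Excluding the null value by such an interval is the same as rejecting in a one-sided test at 2.5%, which is stricter than the planned 5%. A result can therefore pass the test while the interval printed beside it still contains the null.

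The disagreement falls at the weakest result that counts as success. The report could then state that adherence exceeds 60%, or that toxicity is non-inferior, next to an interval that reaches 60% or 90%. Many readers judge non-inferiority by comparing an interval with the margin, and they would say the claim had not been shown. If the interval were taken as the criterion, the power would also be lower than stated. Settling which output governs only after seeing such a result would look post hoc.

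**Working it through.** **Inputs.** Adherence: n = 40, null 60%, alternative 80%, one-sided alpha 0.05, stated power 83% (Sections 7.1 and 7.2). Toxicity: n = 90, null 80% + 10 points = 90%, alternative 80%, one-sided alpha 0.05, stated power 82% (Section 7.2). Assumption: the intervals are two-sided Clopper-Pearson.

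**Step 1: reproduce the stated power.** With X binomial(n, p), find the least extreme count whose tail probability under the null is at most 0.05.

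- Adherence: P(X ≥ 29 | 40, 0.60) = 0.0709 and P(X ≥ 30 | 40, 0.60) = 0.0352, so success is 30 or more. Power = P(X ≥ 30 | 40, 0.80) = 0.839 (stated 83%).
- Toxicity: P(X ≤ 76 | 90, 0.90) = 0.0634 and P(X ≤ 75 | 90, 0.90) = 0.0333, so success is 75 or fewer. Power = P(X ≤ 75 | 90, 0.80) = 0.821 (stated 82%).

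Both figures belong to the one-sided 5% test, as the plan says.

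**Step 2: intervals at and next to the critical counts.** For x events in n, the lower limit is the a/2 quantile of Beta(x, n − x + 1). The upper limit is the 1 − a/2 quantile of Beta(x + 1, n − x). Here a = 0.05 for a 95% interval and 0.10 for a 90% interval.

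| Result | One-sided p | 95% exact interval | 90% exact interval | Null |
|---|---|---|---|---|
| 30/40 | 0.0352 | 58.8% to 87.3% | 61.3% to 85.8% | 60% |
| 31/40 | 0.0156 | 61.5% to 89.2% | 64.0% to 87.7% | 60% |
| 75/90 | 0.0333 | 74.0% to 90.4% | 75.5% to 89.4% | 90% |
| 74/90 | 0.0163 | 72.7% to 89.5% | 74.3% to 88.5% | 90% |

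The 95% interval conflicts with the test at 30/40 and 75/90 only. One count further into the success region they agree. The 90% interval agrees with the test in every row.

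**Step 3: how often the conflict would arise.**

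- If the true rates are 80%: P(X = 30 | 40) = 0.107 and P(X = 75 | 90) = 0.081. As shares of all successes these are 0.107/0.839 = 13% and 0.081/0.821 = 10%.
- If the null is true: 0.020 and 0.017.

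**Step 4: what an interval-based rule would do.** Requiring the 95% interval to exclude the null moves the thresholds to 31/40 and 74/90. Power becomes 0.839 − 0.107 = 0.732 and 0.821 − 0.081 = 0.740. The plan contains no such rule.

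**Step 5: a smaller analysed number.** Section 7.3 limits the analysis to patients with at least four diaries per week, so fewer than 40 or 90 may be analysed. The 5% threshold moves with n. At n = 35 it is 27 adherent (P(X ≥ 27 | 35, 0.60) = 0.026). At n = 80 it is 66 with toxicity (P(X ≤ 66 | 80, 0.90) = 0.027). The exact test as written adapts to this by itself; success counts fixed at 30 and 75 would not.

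**The case for a change.** The case for acting is that the mismatch is real and cheap to remove, and that it does not depend on the particular sample sizes. For analysed numbers from 30 to 40 (adherence) and 70 to 90 (toxicity), there is one conflicting count at every n except 32 for adherence. Aim 1b is an explicit non-inferiority claim, for which comparing an interval with the margin is a natural reading. The adherence result bears on whether a larger study opens (Section 1.2). One line in Section 7.2 calling for 90% intervals, or labelling the 95% intervals descriptive, would prevent an awkward report.

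The arithmetic stands, and so does the observation that the plan does not label the interval. What does not stand is the step from there to an unclear decision. In Section 7.2 only the test carries an alpha and a null value, and the non-inferiority claim is explicitly to be made by the test. The interval accompanies the estimated proportion. The loss of power to 73% and 74% is the consequence of a rule that the plan does not adopt. An interval that reaches 90.4% against a limit of 90% also does not show inferiority; it means only that the stricter 2.5% standard was narrowly missed.

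**Conclusion.** No change is needed. An analyst following Section 7.2 as written reaches a determinate conclusion for each endpoint, with type I error 3.5% and 3.3% at full enrolment and the power that the plan states. The mismatch concerns presentation: one boundary count per endpoint, met with probability 10.7% and 8.1% if the true rates are 80%. Relabelling the interval or adding a 90% interval would change no threshold, error rate, power or conclusion. An analyst can do either when writing the report without amending the plan. Writing in fixed success counts would be a step backwards, because they hold only if all 40 and all 90 patients are analysed.

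This rests on two readings. First, the 95% interval is two-sided; if one-sided bounds were meant (61.3% below, 89.4% above), there is no conflict at all. Second, the exact test is the decision tool, which is the only reading that Section 7.2 supports. Had the plan made the interval the criterion, the stated power would have been wrong and the answer would differ.

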
Objectives
	
The primary objectives are as follows:
 
The study will be conducted in two phases. The first phase will enroll 40 patients. At the end of it, we will determine adherence to CR. We will then proceed to the second phase which will enroll an additional 50 patients, for a total study sample size of 90, and at its end we will assess toxicity, as well as potential predictors of it.
 
Phase 1: Investigate the feasibility of a clinical trial administering ionizing radiation with concurrent CR for the treatment of breast cancer. True adherence will be defined as a successful reduction of 25% of total calories based on diet journals in at least 80% of the logged events.
 
Phase 2: Acute skin toxicity as defined by the National Cancer Institute Common Toxicity Criteria (NCI CTCv.4 for skin reaction, pain and the occurrence of moist desquamation) will be followed to ensure noninferiority as compared with historical controls.
 
The secondary objectives are as follows:
 
Investigate measurable changes of patient characteristics and tissue and serum from fasting/CR conditions to determine a metric for evaluating this treatment in future studies.
 
 • Weight: Weight will be monitored by body mass index, at baseline, week 1, 3, 5 and 7, conclusion and 4 weeks after diet is complete. Body fat measurements via calipers and bioimpedance which will be done at baseline, conclusion and 4 weeks after diet is completed. Vital signs will be monitored weekly. • Serum: 
 • At initiation of diet, conclusion of diet and 4 weeks after diet is complete, fasting labs will be drawn: 
 • Clinical Lab: CBC, basic metabolic panel, hemoglobin A1C, triglycerides, insulin, IGF-1, erythrocyte sedimentation rate (ESR), adiponectin, leptin and estradiol • Other Serum Markers: IGF-1R, IRS-1, proteomic and/or genomic analysis • At week 5: a fasting insulin level will be evaluated. • Psycho-social evaluation: Patients will have psycho-social evaluation using the FACT-B test and the PROMIS cancer fatigue short form at baseline, week 5, conclusion and 4 weeks after conclusion. • Outcomes: Local recurrence, progression free survival, distant metastases and overall survival will be assessed through patient records after study has been completed. • Toxicity: acute skin reaction or pain using the National Cancer Institute Common Toxicity Criteria (NCI CTC) version 4.0 scale²² will be assessed. Number of patients experiencing toxicity and time to occurrence of toxicity will be recorded. This toxicity will be compared to historical controls from TJUH who have also been treated for a 6 – 6.5 week course of radiation.

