7.3 Subject Population(s) for Analysis

All subjects enrolled in the study who completed at least 4 food diaries per week during the diet modification phase will be used for analysis.

8 Safety and Adverse Events

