8.4 Stopping Rules

There will be no formal interim analyses for purposes of stopping the study early. However, descriptive analyses for monitoring accrual and study implementation will be carried out throughout the study.

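### The Aim 1b toxicity test pools patients who did and did not meet the calorie target, so it supports non-inferiority of the diet as advised, not of the diet as followed

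*Combined protocol and SAP*

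**What the plan says.** Section 7.2 (Aim 1b) computes the proportion of patients with toxicity, with a 95% exact interval, and takes the institution's historical rate as about 80%. It then states: "we aim to prove that the dietary intervention is non-inferior with an absolute margin of 10%, using an exact binomial test". The null is therefore a toxicity rate of 90% or more. The stated power is 82% with 90 patients, a true rate of 80% and a one-sided alpha of 0.05.

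Section 3.2 classes each patient as adherent or not, and section 7.2 uses that classification for the adherence endpoint. Aim 1b does not use it. The Study Summary mentions looking at possible predictors of toxicity, but adherence is not named there and 7.2 gives no method for it.

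Section 7.3 defines the analysis set as enrolled subjects "who completed at least 4 food diaries per week during the diet modification phase will be used for analysis". This is a condition on keeping diaries, not on meeting the calorie target.

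On the move between phases, the Study Summary (Objectives) says that adherence is determined after 40 patients and then: "We will then proceed to the second phase which will enroll an additional 50 patients". No adherence result is attached to that step. Section 8.4 adds: "There will be no formal interim analyses for purposes of stopping the study early".

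**The concern.** In a non-inferiority comparison, patients who do not take up the intervention make it look like the control. Here the control is a historical rate of about 80%. A patient who records her intake but does not restrict it should have roughly ordinary radiation toxicity, yet she counts toward the finding that the diet is no worse. If caloric restriction raises skin toxicity, the pooled proportion understates the rise among those who restrict, and the test can pass although their toxicity is at or beyond the margin.

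The protocol treats adherence as an open question. Section 1.2 says it is unknown whether patients can keep to the diet, and Phase 1 tests against a null of 60%. What is at stake is the meaning of a positive Aim 1b result. It would be stated for the dietary intervention, but could partly reflect patients who did not follow it.

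**Working it through.** **Inputs.** Historical rate 80%, margin 10 points, one-sided alpha 0.05, stated power 82% (section 7.2). N = 90 (section 7.1). Phase 1: n = 40, null 60%, alternative 80%, stated power 83% (section 7.1).

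**Reproducing the plan's figures.** The largest c with P(X ≤ c | 90, 0.90) ≤ 0.05 is c = 75. The size is P(X ≤ 75 | 90, 0.90) = 0.0333 and the power is P(X ≤ 75 | 90, 0.80) = 0.821, matching the stated 82%. For Phase 1 the rule is at least 30 of 40 adherent, with size 0.0352 and power 0.839, against the stated 83%.

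**Dilution.** Let a be the share adherent, pA the toxicity rate in adherers and pN the rate in non-adherers. The pooled rate is m = a·pA + (1 − a)·pN, and the chance of declaring non-inferiority is P(X ≤ 75 | 90, m). The documents give neither pA nor pN, so both are assumptions shown over a range. N is held at 90; the 7.3 filter could make it smaller.

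*Non-adherers at the historical rate, pN = 80%:*

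| pA | 100% adherent | 80% adherent | 60% adherent |
|---|---|---|---|
| 90% | m = 90.0%, 3.3% | m = 88.0%, 11.8% | m = 86.0%, 27.4% |
| 92% | m = 92.0%, 0.5% | m = 89.6%, 4.5% | m = 87.2%, 17.2% |
| 95% | m = 95.0%, 0.0% | m = 92.0%, 0.5% | m = 89.0%, 6.7% |

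*Non-adherers with half the diet effect, pN = 80% + (pA − 80%)/2:*

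| pA | pN | 80% adherent | 60% adherent |
|---|---|---|---|
| 90% | 85.0% | m = 89.0%, 6.7% | m = 88.0%, 11.8% |
| 92% | 86.0% | m = 90.8%, 1.7% | m = 89.6%, 4.5% |
| 95% | 87.5% | m = 93.5%, 0.1% | m = 92.0%, 0.5% |

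**Where the pooled rate reaches the limit.** With pN = 80%, m = 90% requires pA = 80% + 10%/a. That is 92.5% at 80% adherence and 96.7% at 60%.

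**Phase 1 at the same adherence levels.** P(at least 30 of 40) is 83.9% at true adherence 80%, 30.9% at 70%, 3.5% at 60% and 0.1% at 50%. As written, Phase 2 enrolls its 50 patients in every case.

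**The same test in adherers only** (null 90%, true rate 80%, one-sided 0.05):

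| Share of 90 | n | Pass if at most | Size | Power |
|---|---|---|---|---|
| 80% | 72 | 59 | 2.5% | 70% |
| 60% | 54 | 44 | 4.0% | 66% |
| 50% | 45 | 36 | 3.2% | 56% |
| 40% | 36 | 28 | 2.4% | 43% |

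**The case against.** *The pooled test is valid.* It is, for the effect of advising the diet whatever the uptake. For that question the error rate stays at 3.3%, and the phrase about the dietary intervention in 7.2 can be read that way. A reader might infer that the test itself is wrong; the documents do not support that. They do not say which effect is meant, and the claim should.

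*Section 7.3 already removes non-adherers.* It removes one kind. Under 3.2 a week with fewer than 4 diaries counts as non-adherent, and 7.3 excludes patients on the same diary count. A patient who logs every week and misses the target every week stays in. Withdrawal for non-compliance under 4.5.1 is discretionary.

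*The assumed effects are severe.* Giving every non-adherer no diet effect is an extreme case, because 3.2 can class as non-adherent someone who restricts substantially but short of 25%. The half-effect table shows how much this matters.

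*The large error rates need poor adherence.* With adherers at 92% and non-adherers at 80%, going down to 50% or 40% adherence gives 27.4% and 39.3%. A reader might take such figures as the size of the problem. The plan assumes 80% adherence, and at 60% or below Phase 1 would almost always miss its threshold, so a published result would show the adherence failure beside the toxicity claim.

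*A larger study would not rest on this result alone.* A reader might infer that a diluted finding would carry straight into the next trial. Sections 1.1 and 1.2 make that trial depend on patients being able to comply. This limits the downstream harm, but it is a statement of intent about the next study and does not alter what Aim 1b will claim.

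*The bias runs one way only if the diet is harmful.* This stands. If restriction lowers toxicity, dilution is conservative.

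**Conclusion.** The point holds in a limited form. The test keeps its 3.3% size for the diet as advised. For the diet as followed, the error rate can exceed 5% if the diet raises toxicity. At the planned 80% adherence this happens when toxicity in adherers is close to the limit: at exactly 90% it is 11.8% with unaffected non-adherers and 6.7% with half-affected ones. It does not happen there at 92% or 95%. At 60% adherence with unaffected non-adherers it is 27.4%, 17.2% and 6.7% for adherer toxicity of 90%, 92% and 95%; with half the effect, only the 90% case (11.8%) stays above 5%. All of these rest on assumed toxicity rates by adherence and on 90 analysed patients.

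This is a gap in what the claim means and in the supporting analysis, not an error in the primary test or its sample size. The remedy is cheap enough to be worth making.

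**What to change.** In section 7.2, Aim 1b:

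- Add a pre-specified supportive analysis that repeats the toxicity proportion, exact interval and exact test in patients classed adherent under 3.2. Report it beside the main result and read it together with the Phase 1 adherence result.
- State that the main test, in the 7.3 population, supports non-inferiority of being advised to restrict calories. State also that if Phase 1 does not meet its own threshold (at least 30 of 40 adherent), the conclusion is limited to that wording.

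The cost is a few sentences and one extra analysis of data already collected, with no added patients or visits. The downside is that the adherent subset is self-selected and smaller. Its power at 80% toxicity ranges from 70% with 72 patients to 43% with 36. It should therefore support the main analysis, neither replacing it nor serving as a second test that must also pass.

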5.7 Prior and Concomitant Therapy

Patients should continue taking their daily medications on a regular basis. Patients should not be taking corticosteroids, anti-retrovirals that would exclude them from participation.

6 Study Procedures

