6.2 Study Visit Schedule

6.2.1 Screening

Eligibility of patients will be verified based on clinical staging and any need for adjuvant chemotherapy as well as previously stated eligibility criteria. Those eligible patients will receive detailed information about the study including a step-by-step outline of proposed treatment including radiation therapy and diet modification. Patients will be informed of possible risks and benefits. Informed consent will be obtained from patients. A full history and physical examination will be performed on consented patients. Baseline weight and BMI will be taken. In addition, blood will be drawn for eligibility measurements of beta-hCG if appropriate.

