6.3 Study Flowchart

Examination	Pre-Treatment					Radiation Treatment								Post RT		Follow-up
	Screening	Surgery	Sim	Week of Caloric Restriction Diet		3	4	5	6	7	8	9	10			
Visit Number	0	1	2	1 3 D7	2 4 D14	5	6	7	8	9	10	11	12 Las t	13		
Informed Consent	X															
Background Info (demographics, meds, medical history)	X															
Inclusion/Exclusion Criteria	X															
Vital Signs			X	X	X	X	X	X	X	X	X	X	X	X		
H&P; Performance Status	X															
Focused Physical			X			X	X	X	X	X	X			X		
Weight, BMI	X		X	X		X		X		X			X	X		
Caliper Measurements, Bioimpedance			X										X	X		

Clinical Labs: CBC w/diff, CMP, HbA1c Serum: IGF-1, adiponectin, leptin, estradiol, triglycerides, fasting insulin, ESR			X											X	X
Fasting insulin level								X							
Other Labs: IGF-1R, IRS-1, FACT-B Psychosocial Evaluation			X											X	X
PROMIS cancer fatigue short form			X					X						X	X
Specimen sent to Pathology for histologic exam andER, PR, HER2		X													
Dietary Counseling	X		X			X	X	X	X	X	X				
Behavioral Counseling				X		X	X	X	X	X	X	X			
Food Diary Collected			X	X	X	X	X	X	X	X	X	X	X	X	
Acute Toxicity Assessment			X			X	X	X	X	X	X	X	X	X	X

Key: H&P=Full history and physical exam
 Sim=Radiation simulation planning session
 RT=Radiation Therapy
 D7=Day 7 of caloric restriction diet; D14=Day 14 of caloric restriction diet
 Last=Final day of caloric restriction diet

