CAREFOR Study**

Current Medication Flowsheet

Date Started	Medication	Indication	Route	Frequency	Dose	Date Stopped

Allergies:

Physician Signature: _____ **Date:** _____

Study : _____ Patient Case No. _____ Time Frame/Cycle #

(circle one): Y or N, N/A

Intermittent RT

Protocol Office AE Toxicity Flowsheet

Date AE Started	Brief Description of Event♦	Numeric Grade CTC 3.0	AEs	Attribution (Related to therapy)	AE Attribution (Potential cause)	Action (Check all that apply)	Outcome
Date:  New  F-U		 0  1  2  3  4	 AE  SAE	 Unrelated  Unlikely  Possible  Probable  Definite	 Chemotherapy  Radiation  Hormone-specify  Other _____	 none required  dose reduced*  dose held*  Adcers  IRB notified  MedWatch 3500A  Other _____	 Resolved End Date: _____  Ongoing
Date:  New  F-U		 0  1  2  3  4	 AE  SAE	 Unrelated  Unlikely  Possible  Probable  Definite	 Chemotherapy  Radiation  Hormone-specify  Other _____	 none required  dose reduced*  dose held*  Adcers  IRB notified  MedWatch 3500A  Other _____	 Resolved End Date: _____  Ongoing

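### The secondary models contain only time, so a drug effect from endocrine therapy or chemotherapy begun during the diet would be read as an effect of caloric restriction

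*Combined protocol and SAP*

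**What the plan says.** The secondary objective (2.2, 3.3) attributes the measured changes to fasting or CR and uses them to pick a yardstick for later studies. Specific Aim 2 (1.2) speaks of a molecular signature of response. The Study Summary describes one arm.

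Section 7.2 plans a paired t-test for body fat and, for weight, "modeling BMI as a function of time (baseline, diet weeks 1, 3, 5, 7, and 10) via mixed-effects regression". For the rest: "The patterns of change over time in vital signs, insulin and other clinical labs, serum markers, and psycho-social outcomes (FACT-B) will also be analyzed similarly". No treatment covariate is named. The only covariate modelling is optional and concerns recurrence and survival: "we may assess the impact of various patient and clinical/treatment variables on these outcomes via Cox proportional hazards regression".

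On concomitant drugs, section 5.7 says "Patients should continue taking their daily medications on a regular basis" and "Patients should not be taking corticosteroids, anti-retrovirals that would exclude them from participation". It mentions neither endocrine therapy nor chemotherapy. Section 6.2.1 says "Eligibility of patients will be verified based on clinical staging and any need for adjuvant chemotherapy as well as previously stated eligibility criteria", but 4.1, 4.2 and the checklists in Appendix VII and Appendix X contain no chemotherapy criterion. Receptor status is obtained (6.3: "Specimen sent to Pathology for histologic exam andER, PR, HER2") but enters no criterion or model.

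The forms in Appendix VII record medication changes with start dates at simulation, at diet days 7 and 14 and during radiation. The medication flowsheet has a stop date.

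**The concern.** In a one-arm before-after comparison, the time coefficient collects everything that changes between the two draws. A drug begun in that interval that moves a marker adds its effect to that coefficient, and nothing in 7.2 takes it out again. More patients do not reduce this bias. They only make it more likely to reach significance.

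The protocol accepts the principle. It excludes patients with HIV because anti-retrovirals may change metabolism (4.1, 4.2), yet it makes no provision for hormonal drugs although estradiol is an endpoint.

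At stake is the choice of metric. A marker that moved because of a drug could be carried into the larger study as a sign of response to CR.

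**Working it through.** **1. The plan's own figures.** Section 7.2 gives no power for the secondary analyses. The primary figures reproduce by exact one-sided binomial tests:

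- Adherence, n = 40, 60% against 80%: success at 30 or more; alpha 0.0352, power 83.9% (stated 83%).
- Toxicity, n = 90, null 80% + 10% = 90%, true rate 80%: non-inferior at 75 or fewer; alpha 0.0333, power 82.1% (stated 82%).

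Neither calculation uses the marker models, so this point does not touch them.

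**2. Apparent estradiol change when CR does nothing.** Assume that a share *f* of patients start a drug between baseline and diet week 10, that it lowers estradiol by a proportion *d* in them, and that all others are unchanged. On the log scale (a transformation 7.2 allows for skewed measures) the mean change is *f* × ln(1 − *d*), so the geometric-mean change is (1 − *d*)^*f* − 1.

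| *f* | *d* = 50% | *d* = 85% |
|---|---|---|
| 10% | -7% | -17% |
| 20% | -13% | -32% |
| 30% | -19% | -43% |
| 50% | -29% | -61% |

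For example, 0.15^0.5 = 0.387, a fall of 61%; 0.50^0.1 = 0.933, a fall of 7%. Both *f* and *d* are assumptions.

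**3. Chance of a significant change when CR does nothing.** This uses different units. Let the drug shift any marker by *D* standard deviations (SD) of the within-patient change. The apparent effect is *f* × *D*, and the SD of change becomes √(1 + *f*(1 − *f*)*D*²). A two-sided paired t-test at 0.05 stands in for the model's contrast of baseline with diet conclusion, with all patients analysable:

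| *f*, *D* | n = 40 | n = 90 |
|---|---|---|
| 25%, 0.25 | 7% | 9% |
| 25%, 0.5 | 12% | 21% |
| 50%, 0.5 | 32% | 62% |
| 50%, 1.0 | 79% | 99% |

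The nominal rate is 5%. For *f* = 50%, *D* = 0.5, n = 90, the shift is 0.25, the SD is √1.0625 = 1.031, and the noncentrality is 0.25 / 1.031 × √90 = 2.30, which gives 62%.

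**4. Price of restricting to unchanged therapy.** The detectable change at 80% power (normal approximation) is (1.960 + 0.842)/√n: 0.30 SD with all 90, 0.34 SD with 68 (*f* = 25%), 0.42 SD with 45 (*f* = 50%) and 0.60 SD with 22 (*f* = 75%).

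**The case against.** The strongest reply is that the premise is not in the documents. They do not say that endocrine therapy is given, when it or chemotherapy starts relative to the diet, or what either does to any marker. A patient on stable therapy at baseline adds no new-start shift. This stands, so the point has to be conditional and its size an illustration.

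A reader might infer more in four places, and the documents do not support it:

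- **That the trial expects these drugs.** The adverse-event flowsheet lists chemotherapy and "Hormone-specify" as potential causes. But it looks like an office template: it grades by CTC 3.0 while the protocol uses version 4, and it has boxes for doses held or reduced. Receptor testing does not show expected use either.
- **That chemotherapy is ignored.** Section 6.2.1 does check the need for it. The gap is that no criterion states the consequence.
- **That the illustration covers every marker.** Step 2 concerns estradiol only. Nothing in the documents sizes a drug effect on IGF-1, triglycerides or BMI.
- **That adjustment would isolate CR.** All patients receive radiation between baseline and diet conclusion, and the protocol's own mouse data (1.2) show radiation alone lowering expression in the IGF-1R pathway. CR would still be confounded with radiation and time.

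It is also fair to say that these are secondary endpoints with no decision rule, and that the envisaged randomized trial could supply concurrent controls. That limits the severity. It does not remove the point, because the metric is to be chosen from these data.

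**Conclusion.** The point holds in conditional form, as a cheap improvement. Endocrine therapy is governed by no listed criterion, and the chemotherapy check in 6.2.1 has no rule behind it. Section 7.2 does not use the medication dates that the forms collect. If patients start such drugs between baseline and diet week 10, any resulting shift is attributed to CR. For estradiol the illustrative size is -7% to -61%, assuming 10% to 50% of patients start, a 50% to 85% fall in those who do, and no CR effect. If no one starts such a drug in that window, this bias is zero.

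Only secondary endpoints are affected. It would be wrong to conclude that the adherence or toxicity test, or its power, is compromised.

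**What to change.** In 7.2, pre-specify a sensitivity analysis of the marker, BMI and FACT-B models limited to patients whose endocrine and cytotoxic therapy did not change between baseline and diet conclusion. Report it beside the all-patient result, and consult it before any marker is proposed as the CR metric. Where numbers allow, add one time-varying term for being on endocrine therapy, built from the recorded start and stop dates. Do not split it by drug class: estradiol, IGF-1, leptin and adiponectin are drawn only three times, and class-specific terms could rest on very few patients.

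State in 7.2 that changes in either analysis remain confounded with radiation and time, and describe them as changes during CR plus radiation.

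Reconcile 6.2.1 with 4.1, 4.2 and both checklists on chemotherapy. What the rule should be is for the investigators.

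The cost is SAP wording, coding of free-text medication entries, and a smaller, less precise subset (step 4). That subset is not a random part of the sample, which is why it should stand beside the main result and not replace it. Chemotherapy for the present cancer that ended before baseline has no dedicated form field, so this analysis would not reliably identify it.
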